8. METHODS OF ASSESSMENT AND ENDPOINTS

All trial data will be recorded on the eCRFs. Timing of study procedures are listed in Section Deleted: Schedule of Assessments. All trial data will be recorded on the eCRFs. Timing of study procedures are listed in schedules of assessments tables – Table 8: Schedule of Assessments (LAM-002A Continuous Monotherapy Administration), Table 9: Schedule of Assessments (LAM-002A Intermittent Monotherapy Administration), Table 10: Schedule of Assessments (LAM-002A/Rituximab Combination Therapy), and Table 11: Schedule of Assessments (LAM-002A/Atezolizumab Combination Therapy) in Section 8.7.

8.1.5. Disease Status Assessment for Subjects with NHL

Pretreatment tumor assessments will be performed within 30 days of the first dose of study treatment and will include diagnostic CT scans (with intravenous contrast) or Positron Emission Tomography (PET)/Computerized Tomography Scans (CT scan) for patients with lymphoma, bone marrow aspirate/biopsy, complete blood counts and physical examination. It is anticipated that in most cases the PET/CT scans will be conducted using a single instrument, i.e., as a PET/CT scan (CT scans should be performed using a contiguous reconstruction algorithm of ≤ 5 mm). However, MRI is an acceptable alternative method for assessing disease in subjects who cannot receive intravenous contrast with CT scans. In such subjects MRI and PET scans will have to be obtained separately.

Suitable scans performed prior to screening and within 30 days before first dose may be used for baseline tumor assessments. Similarly bone marrow biopsies/aspirates performed within 2 months prior to first dose may be used for baseline assessments. For subjects with NHL, baseline bone marrow biopsies/aspirates may be omitted if not deemed essential for response assessment or patient management and there is another source of tumor tissue for pretreatment evaluation of gene expression and prognosis. For subjects with CLL/SLL, a baseline bone marrow aspirate is required unless the presence of sufficient circulating cells in the peripheral blood (e.g., $ALC \ge 10 \times 10^9/L$) permits assessment of baseline parameters for gene expression and prognosis. Details of assessments will be collected on the eCRF and must be filed in the subject's medical record.

Archival tissue from the most recent available biopsy or surgery or fresh tumor tissue (**preferred**) must be obtained pretreatment **for nucleic acid extraction**. For subjects undergoing a biopsy, adequate tumor tissue should be acquired via excisional biopsy, incisional biopsy or core needle biopsy (e.g., ≥ 3 passes using a 16-gauge core needle). Alternatively, cells from a bone marrow aspirate may be obtained in subjects with bone marrow involvement due to NHL ($\geq 50\%$ of cells). Tissue will be submitted for evaluation of the percentage of tumor cells and analysis of genetic alterations and/or gene expression that may predict anti-lymphoma activity and/or pharmacodynamics activity.

In addition, tumor tissue from the most recently availably biopsy or surgery willmay be evaluated for known prognostic characteristics (e.g., for DLBCL: ABC or GCB subtype; expression of BCL2, BCL6, Ki-67, CD20, and MYC; other mutational status), for PDL1 status,

Version 9, 18 Feb 2020

and for immune infiltration. The baseline biopsy procedure (if required) should ideally be performed after the study candidate has undergone the baseline radiology examination and is otherwise considered eligible for study participation..

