1.5 Definitions of Tumor Response and Progression

Responses will be categorized as complete response (CR), partial response (PR), stable disease (SD), or progressive disease (PD). In addition, a response category of nonevaluable (NE) is provided for situations in which there is inadequate information to otherwise categorize response status.

The best overall response will be determined. The best overall response is the best ontreatment response from baseline recorded from the start of treatment until PD/recurrence. The baseline measurement will be taken as a reference for determinations of response. The nadir measurement will be taken as a reference for PD; this measurement constitutes the smallest measurement recorded, including the baseline measurement if this is the smallest measurement. For FDG-avid tumors, metabolic criteria for response by PET-CT will take precedence over anatomic criteria for response by contrast CT when assessing CR.

Version 9, 18 Feb 2020

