7.1. Subject Inclusion Criteria

- 1. The subject is capable of understanding and complying with the protocol requirements and has signed the informed consent document. The subject is able to provide signed and dated informed consent prior to initiation of any study-specific procedures.
- 2. Subjects must have a histologically confirmed diagnosis of B-cell NHL limited to FL, DLBCL, MCL, MZL, **primary mediastinal B-cell lymphoma (PMBL)**, or CLL/SLL according to the World Health Organization (WHO) classification, that has progressed and for which standard curative measures do not exist or are no longer effective. Prior therapy must have included a rituximab based chemoimmunotherapy regimen.
- 3. Subjects with DLBCL must have progressed after transplant, or be unwilling, unable or not an appropriate candidate for an autologous stem cell or bone marrow transplant.
- 4. Subjects must have radiographically measurable lymphadenopathy or extranodal lymphoid malignancy (defined as the presence of ≥ 1 lesion that measures ≥ 2.0 cm in the longest dimension [LD] and ≥ 1.0 cm in the longest perpendicular dimension [LPD] as assessed radiographically).
- 5. The subject is ≥ 18 years old.
- 6. The subject has an Eastern Cooperative Oncology Group (ECOG) Performance Status of ≤ 2.

Version 9, 18 Feb 2020

- 7. The subject has organ and marrow function as follows:
 - a. Absolute neutrophil count (ANC) $\geq 1.0 \times 10^9/L$ (1,000/mm³) without hematopoietic-stimulating factor support
 - b. Platelets $\geq \frac{75}{50} \times 10^9 / L (5075,000 / mm^3)$
 - c. Total bilirubin ≤ 1.5 x the upper limit of normal (ULN) except for subjects with known Gilbert disease (total bilirubin ≤ 3 x ULN permitted)
 - d. Serum creatinine $\leq 1.5 \text{ x ULN}$ or calculated creatinine clearance $\geq 60 \text{ mL/min}$ (based on the Cockcroft-Gault formula)
 - e. Alanine aminotransferase (ALT) and aspartate aminotransferase (AST) \leq 2.5 x ULN if no liver involvement, or \leq 5 x ULN with liver involvement
 - f. Albumin ≥ 2 g/dL

Note: Grade ≥ 3 neutropenia or thrombocytopenia is permitted if the abnormality is related to bone marrow involvement with hematological malignancy (as documented by bone marrow biopsy/aspirate obtained since the last prior therapy).

- 8. The subject has the ability to swallow oral capsules without difficulty.

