7.2 Subject Exclusion Criteria

- 1. Subjects with central nervous system (CNS) lymphoma are not eligible for the trial unless the disease had been treated and the subject remained asymptomatic (for at least 6 months) with no active CNS lymphoma, as determined by lumbar puncture, computed tomography scan (CT), or magnetic resonance imaging (MRI).
- 2. The subject has received cytotoxic chemotherapy (including investigational cytotoxic chemotherapy) within 3 weeks, or nitrosoureas/ mitomycin C within 6 weeks before the first dose of study treatment.
- 3. The subject has received treatment with a therapeutic antibody less than 4 weeks before the first dose of study treatment. For subjects with rapidly progressive or aggressive subtypes of lymphoma, a minimum period of 2 weeks between the last treatment with a therapeutic antibody and the first dose of study treatment may be permitted following discussion with the medical monitor.
- 4. The subject has received radioimmunotherapy within 6 weeks of the first dose of study treatment.
- 5. The subject has received radiation therapy within 14 days of the first dose of study treatment.
- 6. The subject has received prior treatment with a small-molecule kinase inhibitor or other small-molecule investigational agent within 14 days or 5 half-lives of the compound or active metabolites, whichever is greater, before the first dose of study treatment.
- 7. Stage 2 (study candidates being considered for LAM-002A/rituximab combination therapy): Best overall response with the last regimen containing an anti-CD20 antibody (eg, rituximab, ofatumumab, obinutuzumab) was disease progression.
- 8. Stage 2 (study candidates being considered for LAM-002A/atezolizumab combination therapy): Prior exposure to a CD137 agonist or an immune checkpoint inhibitor, including an anti-PD1, anti-PDL1, or anti-CTLA4 therapeutic antibody.
- 9. Stage 2 (study candidates being considered for LAM-002A/atezolizumab combination therapy): treatment with a live, attenuated vaccine within 4 weeks prior to initiation of study treatment, or anticipation of need for such a vaccine during atezolizumab treatment or within 5 months after the last dose of atezolizumab.
- 10. Stage 2 (study candidates being considered for LAM-002A/atezolizumab combination therapy): Current treatment with anti-viral therapy for hepatitis B virus (HBV).

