- B Complete physical examination (PE) will be performed at screening. A directed PE, including weight, will be performed within 72 hours prior to the start of each cycle and EOT.
- C Assessment/test does not need to be repeated on C1D1 if baseline was within normal limits and conducted within 72 hours of first dose.
- D Obtained on Day 1 prior to dosing for all cycles. For C1D1 and C1D8 obtained prior to dosing and 1 hour (± 15 minutes after dosing), 2 hours (± 30 minutes), 4 hours (± 1 hour), and 8 hours (± 1 hour) postdose. For C1D15, obtained prior to dosing.
- E Hematology includes hemoglobin, hematocrit, RBC count, platelet count, WBC and differential.
- F All hematology and chemistry laboratory parameters should be assessed at Screening and Days 1, 8, and 15 of Cycles 1 and 2, and then at least once prior to the start of all subsequent cycles and at EOT. Obtaining a chemistry laboratory parameter on Days 2 and Day 3 of Cycle 1 is only required in subjects with intermediate or high risk of TLS (per the risk definition in Section 6.8.1). Except for Days 1, 2, and 3 of Cycle 1, these parameters may be obtained within 72 hours prior to the planned day of collection. Abnormal test values should be monitored per protocol guidance.
- G Chemistry includes albumin, alkaline phosphatase, total bilirubin, BUN, calcium, carbon dioxide, chloride, creatinine, glucose, inorganic phosphorus, potassium, total protein, LDH, ALT, AST, sodium, and uric acid.
- H Urinalysis includes appearance, specific gravity and pH as well as a semi-quantitative "dipstick" evaluation of glucose, protein, bilirubin, ketones, leukocytes, and blood. Microscopic examination of sediment will be performed if urinalysis is positive for WBC, proteins or blood. Urinalysis may be obtained within 72 hours prior to the planned day of collection.
- I Pregnancy testing (serum or urine) will be required for women of childbearing potential (WCBP) only. Testing is required at Screening; within 72 hours of Day 1 of each cycle and at EOT. Test does not need to be repeated on C1D1 if baseline was negative and conducted within 72 hours of first dose.
- J Imaging as appropriate for disease indication will be conducted within 30 days of the first dose of study treatment. Suitable scans performed prior to screening and within 30 days before first dose may be used for baseline tumor assessments.

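### Some prior therapies may be given after the accepted baseline scan, so carried-over shrinkage can be counted as a LAM-002A response

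*Combined protocol and SAP*

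**What the plan says.** **Baseline imaging.** Section 8.1.5 accepts older scans: "Suitable scans performed prior to screening and within 30 days before first dose may be used for baseline tumor assessments". The imaging footnotes of the monotherapy schedules (Tables 8 and 9) give the same window: "Imaging as appropriate for disease indication will be conducted within 30 days of the first dose of study treatment". Section 11 and the imaging footnotes of Tables 10 and 11 also use 30 days.

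**Washouts (Section 7.2).** The exclusions read:
- Radiation: "The subject has received radiation therapy within 14 days of the first dose of study treatment".
- Small molecules: "The subject has received prior treatment with a small-molecule kinase inhibitor or other small-molecule investigational agent within 14 days or 5 half-lives of the compound", whichever is greater.
- Cytotoxics: "The subject has received cytotoxic chemotherapy (including investigational cytotoxic chemotherapy) within 3 weeks". Nitrosoureas and mitomycin C have 6 weeks.
- Antibodies: 4 weeks. For rapidly progressive or aggressive subtypes, after discussion with the medical monitor, "a minimum period of 2 weeks between the last treatment with a therapeutic antibody and the first dose of study treatment may be permitted".
- Radioimmunotherapy: 6 weeks.

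**Response.** Appendix 2, Section 1.5 says: "The baseline measurement will be taken as a reference for determinations of response". Section 1.5.2 defines partial response for lymphoma chiefly as a fall of at least 50% from baseline in the summed products of the index lesions.

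**Related rules.** The note to inclusion criterion 7 contains the only timing rule tied to earlier treatment. It concerns marrow used to explain cytopenia: "as documented by bone marrow biopsy/aspirate obtained since the last prior therapy". Inclusion criterion 2 requires disease that has progressed, and Section 6.1.2 describes the expansion population as relapsed, progressive and measurable. Appendix 2, Section 1.4.4 allows, but does not require, previously irradiated lesions to be treated as non-index disease.

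**The concern.** The scan window is longer than several of the washouts. A subject can be scanned at Day -30, receive radiation or a short-half-life small molecule until about Day -14, and start LAM-002A without breaching any criterion shown. Shrinkage caused by that earlier treatment is then measured from the Day -30 scan and counted for LAM-002A.

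Stage 2 has no control group in which the same carry-over would appear. Its activity decisions (Section 14.1.2) rest on small response counts: 0/6 in the six-subject cohorts, and lists of n/N values up to 8/20 and 12/20 in the two follicular lymphoma (FL) cohorts. A single misattributed response can matter in each.

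**Working it through.** **1. Overlap in days.** Inputs: the 30-day scan limit (Section 8.1.5), the Day -28 to -1 screening window (Tables 8 to 11) and the washouts (Section 7.2). Overlap = scan age minus washout, with a floor of 0.

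| Prior therapy | Washout (days) | Scan at Day -30 | Scan at Day -28 |
|---|---|---|---|
| Radiation | 14 | 30 - 14 = 16 | 14 |
| Small molecule, 5 half-lives up to 14 days | 14 | 16 | 14 |
| Antibody, by exception | 14 | 16 | 14 |
| Cytotoxic chemotherapy | 21 | 30 - 21 = 9 | 7 |
| Antibody, default | 28 | 30 - 28 = 2 | 0 |
| Nitrosourea/mitomycin C, radioimmunotherapy | 42 | 0 | 0 |

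For small molecules the overlap shrinks as five half-lives exceed 14 days, and is zero at 30 days or more.

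**2. The plan's own decision figures (Section 14.1.2).** Exact one-sided binomial bounds:
- 0/6: upper 90% bound = 1 - 0.1^(1/6) = 31.9%. The plan gives 32%.
- 8/20: lower 95% bound 21.7%. The plan claims at least 20%.
- 12/20: lower 95% bound 39.4%. The plan claims at least 39%.

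These reproduce.

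**3. One response fewer.** 7/20 has a lower bound of 17.7%, below 20%. 11/20 has 34.7%, below 39%. One misattributed response can therefore change the result at full cohort size.

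**4. Fixed-look illustration.** The number of carry-over responders is assumed, because the documents give none. FL monotherapy, true response rate 20%, final count of at least 8/20:
- none: P(X ≥ 8 | 20, 0.2) = 0.032
- one certain carry-over responder: P(X ≥ 7 | 19, 0.2) = 0.068
- two: P(X ≥ 6 | 18, 0.2) = 0.133

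**5. A rate instead of a count.** Let c be the assumed share of true non-responders who appear to respond because of earlier therapy. The apparent rate is 0.2 + 0.8c for monotherapy and 0.39 + 0.61c for the rituximab combination.

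| c | P(≥ 8/20), monotherapy | P(≥ 12/20), combination | P(≥ 1/6) if true rate is 0 |
|---|---|---|---|
| 0 | 0.032 | 0.047 | 0 |
| 2.5% | 0.054 | 0.062 | 0.14 |
| 5% | 0.084 | 0.082 | 0.26 |
| 10% | 0.171 | 0.133 | 0.47 |

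The last column is 1 - (1 - c)^6.

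**6. The rule as planned.** Section 14.1.2 monitors continuously, so steps 4 and 5 do not give its operating characteristics. Applying every listed monotherapy boundary in sequence, with 6/11 at N = 11 (the list gives both 5/11 and 6/11), the chance of crossing at a true 20% is already about 0.081 with no carry-over. With c of 2.5%, 5% and 10% it is about 0.117, 0.161 and 0.272.

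**The case against.** **The population works against the scenario.** Subjects must have progressed disease. Carry-over needs someone who is scanned, receives at most 16 more days of treatment, washes out, and still shows a 50% fall attributable to that treatment just before Cycle 3. A failing therapy that is merely continued would not be expected to do this, and radiation is local while the criterion sums up to six index lesions. This stands as a reason to expect few cases. It does not close the gap: the progression requirement is not tied in time to the last therapy or to the baseline scan, and the non-index option for irradiated lesions is permissive, does not cover systemic therapy, and does not help when irradiation follows index-lesion selection.

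**The bias can run either way.** In progressing disease, growth between an old scan and Day 1 counts against LAM-002A. This stands. The net direction cannot be settled from the documents.

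**Stronger readings that the documents do not support:**
- A reader might infer that the scan window exceeds every washout. The 6-week washouts leave no overlap, and the default antibody overlap is 2 days, or none if the scan falls within screening.
- A reader might apply the 16-day antibody gap to all FL subjects. The exception is confined to rapidly progressive or aggressive subtypes, and Appendix 2, Section 1.4.7 names FL as an example of more indolent disease.
- A reader might extend the point to the 2-month marrow window. Partial response in lymphoma rests chiefly on lesion size, and a positive baseline marrow makes complete response harder to declare. Marrow reduction counts toward partial response only in CLL/SLL, which has no Stage 2 cohort.
- A reader might take 0.032 rising to 0.133 as the error rate of the plan's rule. It describes one final look with an assumed count.

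**The text is incomplete.** The wording of Section 8.1.5 comes from the Amendment 6 change log; the current body is not in the part available. The next amendment changed only paragraphs 3 and 4 of Section 8.1.5, inclusion criterion 11 and exclusion criterion 15 within the sections relied on here, so nothing shown alters the sentence or the washouts.

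**Conclusion.** The point holds as a limited gap in attribution. Following the text shown, prior therapy may fall after the response baseline by up to 16 days (radiation, short-half-life small molecules, antibodies by exception), 9 days (cytotoxics) or 2 days (antibodies by default). No rule found prevents this.

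The day counts and the one-response sensitivity (7/20 against 8/20, 11/20 against 12/20) follow from the documents. The size of any bias does not: the probabilities in steps 4 to 6 rest on assumed carry-over. The documents do not support a claim that the response rates are inflated or the results invalid. They support checking whether any responder was treated after the baseline scan.

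**What to change.** **Now, on data already collected.** Compare each subject's baseline scan date with the date of the last prior anticancer therapy, including radiotherapy. Flag subjects treated after their scan. Report the response rate and the n/N boundary results with and without them. Section 8.1.5 puts assessment details on the eCRF and Section 8.1.3 collects prior cancer treatments, so the cost is a date check and one extra table. This is the more useful half of the remedy, because Version 9 adds an extension stage that can begin once the last subject has completed at least 8 cycles.

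**For any further enrolment.** In Section 8.1.5, Section 11 and the imaging footnotes of Tables 8 to 11, state that the response-baseline scan must be obtained after the last prior anticancer therapy, including radiotherapy, and within 30 days before first dose. No washout needs to change. The cost is a repeat scan for a few subjects and possibly a slightly different response rate. A scan soon after the last treatment would still miss delayed shrinkage, so the date comparison should be kept alongside the rule.

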8.2.4. Electrocardiogram

A 12-lead ECG with subject resting for 5 minutes will be done at Screening. Additional ECGs will be conducted Table 8: Schedule of Assessments (LAM-002A Continuous Monotherapy Administration), Table 9: Schedule of Assessments (LAM-002A Intermittent Monotherapy Administration), Table 10: Schedule of Assessments (LAM-002A/Rituximab Combination Therapy), and Table 11: Schedule of Assessments (LAM-002A/Atezolizumab Combination Therapy) in Section 8.7 prior to the start of each cycle, prior to each PK time point (except for 30 minutes and 6 hours) on Day 1 and Day 8, at the End of Treatment, and more often if clinically indicated. Parameters measured will include heart rate, PR, QRS, QT, and QTc intervals (calculated by the Fridericia correction formula. Bazett's correction is acceptable if institutional policy). See Section 12 for PK time points. The ECGs will be reviewed and signed by the investigator.

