No renal insufficiency has been observed in completed clinical trials to date and no clinically significant safety signals in laboratory, physical examination, or vital sign findings have been noted. One patient with a hematological malignancy receiving the drug at 150 mg BID developed asymptomatic Grade 3 hyponatremia that was attributed to the combined effects of a apilimod-dimesylate-induced diarrhea and hydrochlorothiazide administration.

Cardiac monitoring in clinical studies to date has not revealed any major issues. However in a thorough QT/QTc study, apilimod dimesylate at doses of 50 mg and 150 mg was associated with repolarization findings in excess of those deemed negative by International Conference on Harmonisation (ICH) E14 guidance. The magnitude of the change was modest (~8.5 msec) and the root-mean-square based analyses did not demonstrate as large an increase in cardiac repolarization time (≤ 1.22 msec) as that identified using the Fridericia method. Therefore the significance of this finding is unclear. **Preliminary QTc observations in the ongoing study in patients with hematological malignancies suggest the potential for dose- and exposure-dependent Grade 1 or 2 QT prolongation.**

Version 9, 18 Feb 2020

In totality, the nonclinical and clinical data collected to date support the exploration of apilimod dimesylate in patients with NHL.

Section 4.1.6. Previous Clinical Experience with Apilimod and Apilimod Dimesylate in Nonmalignant Conditions

Change: The title of the section has been clarified, as noted above.

SECTION 6 INVESTIGATIONAL PLAN

Changes: Information in Subsections 6.1, 6.2, and 6.5 regarding the dose-escalation and sample sizes has been updated to reflection inclusion of additional dose levels and schedules.

Subsection 6.4.3,1 has been clarified to indicate that all subjects will be followed for survival and to provide additional information regarding out how that follow-up will be performed.

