6.9.7. Drugs Known to Prolong the QT Interval

In a thorough QTc study, apilimod dimesylate at doses of 50 mg and 150 mg was associated with repolarization findings in excess of those deemed negative by regulatory guidance. The magnitude of the change was modest (~8.5 msec), peaked at 4 hours and did not demonstrate a dose trend. Preliminary QTc observations in the ongoing study in patients with hematological malignancies suggest the potential for dose- and exposure dependent Grade 1 or 2 QT prolongation.

As a precaution, the clinical potential of LAM-002A to prolong the QT interval will be assessed in this study. Accordingly, co-administration of LAM-002A and known QT-prolonging drugs is to be minimized because use of such drugs might confound interpretation of QT data from the trial.

Based on these considerations, protocol candidates who require therapy with drugs known to prolong the QT interval (as listed in Table 15) should not be enrolled into the study. If medically justified, protocol candidates may be enrolled if such drugs can be discontinued or alternative drugs that do not affect QT can be substituted >7 days before the first dose of study drug.

After the subject is enrolled to the protocol, use of drugs known to prolong the QT interval should be minimized but is not prohibited if administration of such drug is necessary and the subject appears to be benefiting from protocol therapy.

Version 9, 18 Feb 2020

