- Stage 2 (study candidates being considered for LAM-002A/atezolizumab **17.** combination therapy): Active or history of autoimmune disease or immune deficiency, including, but not limited to, myasthenia gravis, myositis, autoimmune hepatitis, systemic lupus erythematosus, rheumatoid arthritis, inflammatory bowel disease, antiphospholipid antibody syndrome, Wegener granulomatosis, Sjögren syndrome, Guillain-Barré syndrome, or multiple sclerosis (with the following exceptions: history of autoimmune-related hypothyroidism and receiving thyroid-replacement hormone; controlled Type 1 diabetes mellitus on an insulin regimen; eczema, psoriasis, lichen simplex chronicus, or vitiligo with dermatologic manifestations if rash covers covers < 10% of body surface area, disease is well controlled at baseline and requires only low-potency topical corticosteroids, there is no occurrence of acute exacerbations of the underlying condition requiring psoralen plus ultraviolet A radiation, methotrexate, retinoids, biologic agents, oral calcineurin inhibitors, or high-potency or oral corticosteroids within the previous 12 months, and the subject does not have extra-cutaneous disease [e.g., psoriatic arthritis]).

Version 9, 18 Feb 2020

- 18. The subject has a history of malabsorption or other GI disease that may significantly alter the absorption of apilimod (e.g., \geq Grade 2 nausea, vomiting or diarrhea).
- 19. The subject has undergone major surgery within 28 days prior to first dose of study drug.
- 20. The subject has a QTcF > 470 msec on screening ECG or has a history or risk factors for, or use of medications known to prolong QTc interval or that may be associated with Torsades de Pointes within 7 days of treatment start.
- 21. The subject has past history of tuberculosis (TB) or active infection with TB, human immunodeficiency virus (HIV), hepatitis B virus (HBV) or hepatitis C virus (HCV). Note: Subjects must have negative human immunodeficiency virus (HIV) antibody, negative hepatitis B surface antigen (HbsAg) and negative hepatitis B core (HBc) antibody or undetectable HBV deoxyribonucleic acid (DNA) by quantitative polymerase chain reaction (PCR) testing, and negative HCV antibody or negative HCV ribonucleic acid (RNA) by quantitative PCR.
- 22. The subject is lactating and breast feeding.
- 23. The subject has a previously identified allergy or hypersensitivity to components of the study treatment formulation.

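### Section 8.2.4 lets site policy substitute Bazett for Fridericia QTc, so absolute QTc values, outlier counts and the screening comparison depend on site and heart rate, although QTcF can be derived for every ECG

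*Combined protocol and SAP*

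**What the plan says.** Section 8.2.4 (Electrocardiogram), as displayed under Amendment 6, names Fridericia as the QTc correction and then adds that Bazett's "correction is acceptable if institutional policy". Just before this it lists what is recorded: "Parameters measured will include heart rate, PR, QRS, QT, and QTc intervals". The section closes with review at the site: "The ECGs will be reviewed and signed by the investigator". It mentions neither central reading nor re-derivation of QTc.

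Section 6.9.7 (Drugs Known to Prolong the QT Interval) makes QT a question for this trial: "the clinical potential of LAM-002A to prolong the QT interval will be assessed in this study". It cites a prior thorough QTc study at 50 mg and 150 mg: "The magnitude of the change was modest (~8.5 msec), peaked at 4 hours and did not demonstrate a dose trend". It also says that preliminary observations in the present trial "suggest the potential for dose- and exposure dependent Grade 1 or 2 QT prolongation".

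The background safety text displayed under Amendment 4 ties the result of that thorough QTc study to one formula. A root-mean-square analysis did not show as large an increase "as that identified using the Fridericia method".

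Section 7.2, exclusion criterion 20, sets the screening limit on the Fridericia scale: "The subject has a QTcF > 470 msec on screening ECG".

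**The concern.** Bazett and Fridericia agree only at 60 bpm. Above that Bazett reads higher, and below it reads lower. If the formula follows institutional policy, two subjects with the same QT and heart rate can carry different QTc values because they attend different sites.

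Three things are exposed:

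- **Absolute QTc and outlier counts.** A fast heart rate at a Bazett site can push a value over a limit that the Fridericia value does not reach.
- **The screening comparison.** Criterion 20 is in QTcF, but 8.2.4 allows a site to report something else.
- **Any look at dose or exposure.** Escalation cohorts hold 3 to 6 subjects (Section 14.1.1), so one Bazett site in one cohort could alter the apparent pattern. The prior ~8.5 msec finding is a Fridericia result, and Bazett values are not comparable with it.

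**Working it through.** **Inputs.** From the documents: the ~8.5 msec change (Section 6.9.7), obtained with Fridericia (background safety text, Amendment 4), and the 470 msec QTcF limit (Section 7.2, criterion 20). The 8.5 msec is an external result given without data, so there is nothing to reproduce. The documents give no heart-rate or QTc distribution. Assumed ranges: heart rate (HR) 50 to 100 bpm, QTcF 400 to 470 msec.

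**Formulas.** With RR = 60/HR in seconds, QTcB = QT/RR^(1/2) and QTcF = QT/RR^(1/3). Hence QTcB = QTcF × (HR/60)^(1/6), and the difference is QTcF × [(HR/60)^(1/6) − 1].

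**Step 1: difference in level (QTcB minus QTcF, msec).**

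| HR (bpm) | QTcF 400 | QTcF 420 | QTcF 470 |
|---|---|---|---|
| 50 | −12.0 | −12.6 | −14.1 |
| 55 | −5.8 | −6.0 | −6.8 |
| 60 | 0.0 | 0.0 | 0.0 |
| 65 | +5.4 | +5.6 | +6.3 |
| 70 | +10.4 | +10.9 | +12.2 |
| 80 | +19.6 | +20.6 | +23.1 |
| 90 | +28.0 | +29.4 | +32.9 |
| 100 | +35.5 | +37.3 | +41.8 |

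**Step 2: where the difference passes 8.5 msec.** Upper limit: HR = 60 × (1 + 8.5/QTcF)^6, which gives 68.1 bpm at QTcF 400 and 66.8 at QTcF 470. Lower limit: HR = 60 × (1 − 8.5/QTcF)^6, which gives 52.7 and 53.8 bpm. Between these limits the difference is below 8.5 msec.

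**Step 3: screening.** The QTcF that corresponds to a Bazett reading of 470 is 470/(HR/60)^(1/6): 484.5 msec at 50 bpm, 470.0 at 60, 458.1 at 70, 448.0 at 80, 439.3 at 90 and 431.6 at 100. A Bazett reading held against the 470 limit is thus stricter than the written criterion above 60 bpm and more lenient below it.

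**Step 4: change within a subject, Bazett throughout, baseline QTcF 420.**

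- Heart rate unchanged: a true QTcF rise of 8.5 msec reads 8.5, 8.7, 8.9 and 9.1 msec on Bazett at baseline heart rates of 60, 70, 80 and 90. The offset almost cancels.
- No true QTcF change: a false rise of 8.5 msec needs a heart-rate rise d that solves 420 × [((b + d)/60)^(1/6) − (b/60)^(1/6)] = 8.5, where b is the baseline rate. This gives d = 7.7, 8.7, 9.7 and 10.7 bpm for b = 60, 70, 80 and 90.
- Heart rate falls by 10 bpm: a true rise of 8.5 msec reads −4.3, −2.4, −1.0 and +0.2 msec at the same baselines, so it can be hidden as well as imitated.

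**The case against.** Four points on the other side have weight.

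**The text is an amendment display.** Section 8.2.4 is seen as printed in the Amendment 6 changes, where insertion and deletion marking has been lost, and the main body of the protocol is not in the part of the document available here. The sentence could have been struck. Against that, Amendment 6's stated reasons for changing Section 8 do not mention QTc. Of the two later amendments displayed, one moves from 8.1.5 to 8.3.1.3 and the other from the opening of Section 8 to 9.1.6. Retention is likely but not proved.

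**No analysis is shown to pool the two scales.** A rule that derives QTcF for every ECG may exist in text not seen. This stands, and the point concerns what 8.2.4 permits, not a demonstrated analysis error.

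**The size depends on heart rate.** A reader might infer that the formula difference always exceeds the QT effect under study. It does not: it is zero at 60 bpm and under 8.5 msec from about 54 to 67 bpm. Nor is 8.5 msec a target effect for this trial. It is a change observed in an earlier study, while the figures in Step 1 are differences in level.

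**Most of the offset cancels in change from baseline** if a subject stays on one formula and heart rate is steady. This also stands. Nothing in the documents says that the drug raises heart rate.

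It may also be said that editing 8.2.4 now achieves little, because Stage 3 collects only serious adverse event reports on fewer than four subjects. That holds for new ECGs. It does not apply to a derivation in the dataset for ECGs already recorded.

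**Conclusion.** The point holds in limited form. As displayed, 8.2.4 lets institutional policy choose the QTc scale in a trial that says it will assess QT prolongation and that screens on QTcF. Absolute values, outlier counts and the screening comparison are exposed. The difference exceeds the cited ~8.5 msec above about 67 to 68 bpm or below about 53 bpm, and reaches about 36 to 42 msec at 100 bpm. This assumes QTcF of 400 to 470 msec and rests on no heart-rate data from the trial.

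A reader might go further and conclude that QTc changes from baseline are generally biased, or that the dose-exposure assessment is already compromised. The documents do not support that. Change is affected mainly when heart rate shifts by about 8 to 11 bpm or more, and neither the number of Bazett sites nor the analysis actually used is known. Confidence is moderate because the current body text could not be checked. The change is worth making because the inputs are already recorded.

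**What to change.** 1. In 8.2.4, remove the Bazett allowance for trial data. A Bazett value printed by the site may stay in the source record.
2. Record uncorrected QT and heart rate on the eCRF and derive QTcF = QT/(60/HR)^(1/3) programmatically for every ECG, including those already collected, before the database lock that precedes Stage 3.
3. Use the derived QTcF in every QTc summary, outlier table and dose or exposure display. If only Bazett QTc and heart rate were captured for an ECG, QTcF can be recovered as QTcB/(HR/60)^(1/6); if heart rate is missing too, flag the value and keep it out of pooled summaries.
4. Reconcile 8.2.4 with criterion 20, which already names QTcF, so that screening values are on the scale of the written limit. The limit itself is not in question here.
5. If the protocol body or the statistical section already contains such a derivation, a cross-reference in 8.2.4 is enough.

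The cost is one derivation in the dataset and a completeness check on QT and heart rate. No new procedure or visit is needed, and the between-formula difference becomes zero at every heart rate.
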